In Phase 2 studies, the pharmacodynamic effect of relamorelin was confirmed in larger numbers of participants with DG, and in addition, beneficial effects on the symptoms of DG were observed. Safety and tolerability were shown at therapeutic doses, including the 10 µg twice daily (BID) dose to be studied in Phase 3 studies, supporting the decision to obtain confirmatory evidence of safety and efficacy of relamorelin in Phase 3, and specifically in Study RLM-MD-02.

A significant unmet medical need exists for a safe and effective treatment of patients with DG whose quality of life is impacted by their disease and for whom the current standard of care is suboptimal; therefore, the sponsor is performing this study to further the development of relamorelin for the treatment of DG.

Relamorelin

Objectives and Endpoints:

Objectives	Endpoints

Primary
 
 To compare the efficacy of relamorelin with placebo in participants with DG with respect to a composite of the following core signs and symptoms of DG: 
 Nausea Abdominal pain Postprandial fullness Bloating To compare the efficacy of relamorelin with placebo in participants with DG with respect to vomiting frequency 	
 Change from Baseline to Week 12 in the weekly DGSSS. Baseline is defined as the average of the 2 weekly DGSSS from the 2-week placebo Run-in Period. Vomiting Responder, defined as a participant with zero weekly vomiting episodes during each of the last 6 weeks of the 12-week Treatment Period

Secondary
 
 To compare the efficacy of relamorelin with placebo in participants with DG with respect to the following individual symptoms of the DGSSS: 
 Nausea Abdominal Pain Postprandial fullness Bloating To compare the safety of relamorelin with placebo in participants with DG 	
Secondary
 
 Individual Symptom (ie, nausea, abdominal pain, postprandial fullness, and bloating) Responder, defined as a participant with at least a 2-point decrease in the change from baseline on the weekly average of the symptom severity (at its worst) during each of the last 6 weeks of the 12-week Treatment Period AEs, clinical laboratory values, vital signs, ECGs, HbA1c, and anti-relamorelin antibodies

Overall Study Design:

- Global, multicenter, randomized, double-blind, placebo-controlled, parallel-group

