- After Run-in Period: Evidence of compliance during the Run-in Period with the use of the electronic hand-held device for entry of data, with twice daily SC injections of the study treatment, no treatment with GI promotility agents during the Run-in Period, at least 1 vomiting episode reported during the 2-week Run-in Period, and a score of \geq 16 for the average of the daily Diabetic Gastroparesis Symptom Severity Score (DGSSS) assessments measured during the Run-in Period.

Number of Sites:

[figure not shown]
Approximately 350 sites (globally)

██████████
Relamorelin

[figure not shown]
██████████
Relamorelin

A large, solid black rectangular redaction box covers the majority of the page content, starting below the word "Relamorelin" and extending nearly to the bottom and sides of the page.

[figure not shown]
██████████
Relamorelin

A large, solid black rectangular redaction box covers the majority of the page content, starting below the word "Relamorelin" and extending nearly to the bottom of the page.

██████████
Relamorelin

██████████
Relamorelin

Relamorelin

3. Introduction

Relamorelin (also known as RM-131) is a novel, potent, and selective synthetic penta-peptide ghrelin analogue, which is being developed for treatment of diabetic gastroparesis (DG).

Ghrelin, a 28 amino-acid peptide, is produced predominantly by specialized cells of the stomach and pancreas, and has been demonstrated to be a central modulator of energy homeostasis. It is the natural ligand for the Growth Hormone Secretagogue 1 α (GHS1 α) receptor, a potential target for treatment of clinical conditions associated with impaired gastric motility and energy balance. Administration of ghrelin has been shown to promote gastric motility in mice, rats, dogs, and humans ([Dornonville 2004](#); [Trudel 2003](#); and [Murray 2005](#)). It can increase body weight, attributed to a combination of enhanced food intake, increased gastric emptying (GE), and increased food assimilation, coupled with a transient increase in growth hormone (GH), which promotes nutrient incorporation into tissues.

Relamorelin has similar characteristics to native ghrelin but with enhanced efficacy, plasma stability, and circulating half-life. As a ghrelin mimetic, it acts as a potent prokinetic agent, as evidenced by significant effects on GE as well as effects on overall colonic transit ([Acosta 2015](#), [Acosta 2016](#)).

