7.3. Method of Treatment Assignment

All participants will be centrally assigned to randomized study treatment using an interactive web response system (IWRS). Before the study is initiated, the log-in information and directions for the IWRS will be provided to each site.

At the beginning of the 12-week Treatment Period, eligible participants will be randomized in a 1:1 ratio to blinded treatment with relamorelin 10 µg or placebo. Randomization will be stratified by geographic region.

Study treatment will be dispensed at the study visits indicated in the Schedule of Activities (SoA) (Section 2).

Returned study treatment should not be re-dispensed to the participants.

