10.3.1. Key Statistical Methodology

The methodologies defined in [Table 10-2](#) apply as specified to individual endpoints defined in this protocol. All statistical tests will be 2-sided hypothesis tests performed at the 5% level of significance for main effects. All CIs will be 2-sided 95% CIs, unless stated otherwise.

Table 10-2: Statistical Methodology

Methodology	Description
Categorical counts	
 Number of participants in individual categories 
 Participants with ≥ 1 qualifying event counted once per individual category
Categorical descriptives	
 Number and percentage of participants in individual categories 
 Participants with ≥ 1 qualifying event counted once per individual category N1 if percentage denominator \neq number of participants in the population (standard percentage denominator) 
 N1 = participants with nonmissing baseline value
Event descriptives	
 Number and percentage of events in individual categories 
 Events counted individually for each instance Percentage denominator = total number of events
Continuous descriptives	
 N1, mean, SD, median, minimum, maximum N1 = participants with nonmissing value
CFB descriptives	
 Continuous descriptives for baseline, postbaseline, and change from baseline (CFB) values N1 = participants with nonmissing values at both baseline and the specified postbaseline analysis visit
Responder	
 Categorical descriptives for responders and nonresponders 
 Nonresponders include: 
 Participants who do not meet responder criteria Participants with no postbaseline values Risk differences and Wald CIs vs [placebo/active comparator] Estimates derived from Cochran-Mantel-Haenszel (CMH) model controlling for factors (treatment group, region) 
 Mantel-Haenszel (MH) odds ratios (ORs) and CIs vs placebo P-values comparing treatment group vs placebo N1 = all participants unless otherwise specified

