10.0 Efficacy Analyses

The efficacy analyses will be based on the mITT Population.

Most efficacy parameters will be derived from the DGSSD, a 7-item, patient-reported daily diary designed to assess the severity of 6 core signs and symptoms of DG—nausea, abdominal pain, postprandial fullness, bloating, vomiting, and early satiety—and the frequency of vomiting episodes (Appendix 1). For purposes of the analyses, weekly values will be calculated from the daily e-diary data as described in Section 16.3 of this SAP. For weeks with less than 4 days of available DGSSD data, weekly values will be set to missing.

Baseline values for parameters are derived from the DGSSD collected in the Run-in period, (ie, *Diabetic Gastroparesis Symptom Severity Score (DGSSS: sum of nausea, abdominal pain, postprandial fullness, and bloating), nausea, abdominal pain, postprandial fullness, bloating, early satiety, vomiting frequency and vomiting severity*) following the steps below:

- Weekly value for Week -2 and Week -1 will be the average value of DGSSD in the week (See the analysis week definition for Week -2 and Week -1 in Section 16.2.1);
- Baseline will be the average of the two weekly values of Week -2 and Week -1.

All statistical tests will be 2-sided hypothesis tests performed at the 5% level of significance for main effects. All confidence intervals will be 2-sided 95% confidence interval, unless stated otherwise.

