10.1.1 Primary Analysis

10.1.1.1 Change from Baseline to Week 12 in the Weekly DGSSS

The primary efficacy parameter, the change from baseline to Week 12 in the weekly DGSSS, will be analyzed using a longitudinal, mixed-effects model with repeated measures (MMRM) approach.

The MMRM model will include fixed effects for geographic region, treatment, week, treatment-by-week interaction, as well as baseline and baseline-by-week interaction values as the covariates with unstructured variance-covariance matrix being common to all participants for the repeated measures over weeks. In case the model will not converge with the unstructured covariance structure, the Toeplitz structure (TOEP) will be used instead. Least square (LS) mean changes from baseline for each treatment group, and LS mean difference between RLM group and placebo group, and the associated 95% confidence interval for the difference will be provided, along with the reported p-values (two-sided).

In addition, cumulative distribution function plot will be presented for the change from baseline to Week 12 in the Weekly DGSSS for each treatment group.

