10.1.1.2 Vomiting Study Responder (V-SR)

For the primary efficacy responder parameter V-SR, the proportion of responders in the RLM group and the placebo group will be analyzed by the Cochran-Mantel-Haenszel (CMH) test controlling for geographic region. The number, percentage, and the 95% confidence interval for the percentage of Responders by treatment group, the difference in responder rates between the RLM and the placebo group and its corresponding 95% confidence interval, and the 2-sided p-value associated with the above CMH test will be presented. The Mantel-Haenszel estimate of odds ratio (RLM divided by Placebo) - controlling for geographic region- and the corresponding 95% confidence interval will also be provided.

A participant will be considered a vomiting study non-Responder (ie not a V-SR) if the weekly number of vomiting episodes is missing for any of the last 6 weeks of the 12-week Treatment Period.

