16.11 Definition of Regions and Pooling

Geographic regions are used as randomization strata factor and include: Asia, Australia/New Zealand, Eastern Europe, North America, Western Europe, Latin America, Middle East and Africa. Depending on actual participant enrollment, the list of regions will be subject to change.

It is expected that sample sizes will be adequately large for each strata. In case the smallest region has less than 8 participants with post-baseline DGSSD assessments then it will be pooled for purposes of analyses, with the second smallest region. If the resulting regions do not all have the minimum number of participants, the process will continue until the minimum number requirement is met. Pooling of regions -if any- will be performed prior to the study unblinding.

17.0

Changes to Analyses Specified in Protocol

None.

18.0

References

Knobe J (1991). Nonparametric Analysis of Covariance for Comparing Change in Randomized Studies with Baseline Values Subject to Error. *Biometrics*, 47(2):523-533.

Ratitch B, and O'Kelly M. (2011). Implementation of Pattern-Mixture Models Using Standard SAS/STAT Procedures.. *In Proceedings of PharmaSUG 2011 (Pharmaceutical Industry SAS Users Group)*. Paper SP04. Nashville.

Rubin, D.B. Multiple Imputation for Nonresponse in Surveys. New York: John Wiley & Sons. 1987;75-77:169-170.

Electronic Signatures

User	Date	Justification
	17-Nov-2020 16:45:21 (GMT)	Manager Approval
	17-Nov-2020 14:24:09 (GMT)	Subject Matter Expert Approval
	17-Nov-2020 15:15:40 (GMT)	Subject Matter Expert Approval
	17-Nov-2020 14:00:10 (GMT)	Document Originator Approval
	17-Nov-2020 14:39:05 (GMT)	Subject Matter Expert Approval

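### Cheap improvement, not an error: the primary Vomiting Responder test controls for region only, although a run-in vomiting baseline is already collected and derived

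*Protocol*

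**What the plan says.** The endpoint, in protocol Sections 1 and 4, is "Vomiting Responder, defined as a participant with zero weekly vomiting episodes during each of the last 6 weeks of the 12-week Treatment Period". Run-in entry requires "at least 1 vomiting episode reported during the 2-week Run-in Period" (protocol Sections 1 and 5.1).

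On assignment, protocol 7.3 says "Randomization will be stratified by geographic region", and SAP 16.11 agrees: "Geographic regions are used as randomization strata factor". On analysis, SAP 10.1.1.2 says the responder proportions "will be analyzed by the Cochran-Mantel-Haenszel (CMH) test controlling for geographic region". The responder row of protocol Table 10-2 names treatment group and region as the factors. Step 3 of the imputation analyses (SAP 10.1.2.1) reuses the same method.

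A vomiting baseline exists. Protocol 9.1.1.2 captures vomiting frequency during the run-in, and SAP 10.0 lists "early satiety, vomiting frequency and vomiting severity" among the parameters whose baseline is the average of Weeks -2 and -1. For the other primary parameter, SAP 10.1.1.1 fits a repeated-measures model with region, treatment, week and their interaction, "as well as baseline and baseline-by-week interaction values as the covariates".

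**The concern.** The target is absolute. A participant who vomited once in two weeks and one who vomits daily must both reach zero for six weeks, so the starting frequency plausibly affects the chance of success. Unlike the DGSSS change or the 2-point item responders, this endpoint contains no baseline value. The plan adjusts one primary endpoint for its baseline and leaves the other unadjusted, and the public text gives no reason for the difference.

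What is at stake is precision on H2. Under SAP 10.1, rejecting either primary hypothesis meets the primary objective. Under SAP 10.3, rejecting only one of the two cuts the alpha for the four symptom tests from 0.05 to 0.0125. Precision on H2 therefore also affects the secondary family.

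**Working it through.** **Inputs from the documents.** 300 per arm (protocol 5.2); 26% vs 11% responders (SAP 14.0); 20% dropout by Week 12, stated there for the DGSSS simulation; a missing week in Weeks 7-12 makes a non-responder (SAP 10.1.1.2); two-sided truncated Holm with first level 0.025 (SAP 10.3), critical z = 2.241.

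**Assumed inputs.** The documents give neither the distribution of run-in vomiting nor its prognostic strength, so both are varied below.

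**1. The plan's own figure.** The plan states more than 90% power to reject at least one primary hypothesis. For H2 alone, power = Φ[(d − z·SE0)/SE1], with SE0 = √(2p̄(1−p̄)/n) and SE1 = √((p1q1 + p2q2)/n).
- 26% vs 11%: SE0 = 0.03170, SE1 = 0.03111; (0.15 − 2.241 × 0.03170)/0.03111 = 2.54, so power is 99.4%.
- Dropouts as non-responders: 0.26 × 0.8 = 20.8% and 0.11 × 0.8 = 8.8%; SE0 = 0.02899, SE1 = 0.02858; (0.12 − 2.241 × 0.02899)/0.02858 = 1.93, so power is 97.3%.

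The stated figure holds as a lower bound on H2 alone. The DGSSS simulation cannot be rerun, because its covariance table is not in the public text.

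**2. Validity.** Simulation of 600 participants in seven regions (shares assumed), 4,000 runs per scenario. Baseline vomiting was a standardised covariate with an assumed log-odds slope of 0 to 2 per SD. With 11% in both arms, the region-only CMH test rejected in 2.2% to 2.7% of runs, and the region-by-tertile test in 2.2% to 2.7%, against a nominal 2.5%. Both hold their level.

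**3. Power in the same simulation** (alpha 0.025; region only → region by tertile):

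| True rates | Slope 0 | Slope 1 | Slope 1.5 | Slope 2 |
|---|---|---|---|---|
| 26% vs 11% | 99.4 → 99.3% | 99.5 → 99.8% | 99.5 → 99.8% | 99.3 → 99.95% |
| 20.8% vs 8.8% | 97.7 → 97.5% | 97.9 → 98.3% | 97.2 → 98.6% | 97.8 → 99.1% |
| 20% vs 11% (assumed) | 80.5 → 79.5% | 78.6 → 81.2% | 79.6 → 85.1% | 80.0 → 87.7% |

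The Monte Carlo standard error near 80% is √(0.8 × 0.2/4000) = 0.6 points per entry.

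**4. A smaller effect, modelled from vomiting counts.** Assume 18% vs 11%, with dropouts already counted as non-responders. Then z = 0.07/√((0.18 × 0.82 + 0.11 × 0.89)/300) = 0.07/0.02861 = 2.447, and power = Φ(2.447 − 2.241) = 58%.

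For the gain, 18 scenarios were run. Weekly vomiting rates were gamma (shape 0.5, 1 or 2; mean 3 or 6 per week before selection). The two-week run-in count was Poisson with at least 1 required. The on-treatment rate was the baseline rate times a lognormal multiplier (log SD 0, 1 or 2). Dropout was 20%, and region was not modelled. The ratio of the CMH noncentrality with run-in tertiles to that without, minus 1, ranged from 2% to 25%, median about 8%. Scaling z by the square root of the gain:
- 2%: Φ(2.447 × √1.02 − 2.241) = 59%
- 8%: Φ(2.447 × √1.08 − 2.241) = 62%
- 25%: Φ(2.447 × √1.25 − 2.241) = 69%

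**5. Chance imbalance.** At the planned rates, with slopes of 0.5 to 2, chance imbalance in the baseline moves the rate difference with an SD of 0.6 to 1.9 points. The standard error of the difference is about 3.1 points and already includes this.

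**The case against.** The strongest reply is that a CMH test stratified by the randomisation factor is prespecified, valid and matched to the design, and that at the planned rates nothing is lost. That stands. A visible benefit needs an effect well below the planned 15 points. Even then, if H1 is rejected first, H2 is tested at 0.0375, where power at 18% vs 11% without adjustment is already about 64%.

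It is also fair that prognostic strength is not documented. The 18 count scenarios build it in, so none can show zero gain; the slope-0 column in step 3 covers that case. Protocol 3.2 reports that vomiting fell by about 70% on placebo in Phase 2b, which makes it less certain that a two-week count predicts Weeks 7-12. The same passage also makes a smaller effect realistic, since the fall on relamorelin was about 75%.

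SAP 10.4 is not in the public text, so a supportive adjusted analysis cannot be ruled out. It would not change the primary test, which SAP 10.1.1.2 states in full.

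Three stronger readings are tempting. A reader might infer that the region-only test is biased or inflates type I error; step 2 shows that it does not. A reader might infer that the sample size is inadequate; step 1 shows that it is not. A reader might infer that randomisation should have been stratified by vomiting; adjustment in the analysis recovers the precision, and step 5 shows that chance imbalance is already within the standard error.

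**Conclusion.** The point holds as an efficiency improvement. The gain is at most about 0.6 points of power at 26% vs 11%, and 0 to about 1.5 points at 20.8% vs 8.8%. At an assumed 18% vs 11% it is worth 2% to 25% more participants (median about 8%), or 58% power becoming 59-69%. With a non-prognostic baseline there is no gain and no material loss: at most about 1 point in the slope-0 column, against the Monte Carlo error of 0.6 points per entry.

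These sizes rest on an assumed distribution of run-in vomiting and an assumed link between run-in and later vomiting. That the baseline is prognostic is a reasonable inference from the endpoint, not a documented fact. SAP 4.0 records early termination and only descriptive efficacy analyses, so the point applies to the confirmatory analysis as planned.

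**What to change.** In SAP 10.1.1.2 and protocol Table 10-2, for the Vomiting Responder:
- Form the CMH and Mantel-Haenszel strata from region and baseline vomiting-frequency group, for example tertiles, with cut points fixed on blinded pooled data before unblinding.
- Apply the pooling rule of SAP 16.11 with region-by-group cells in view. A region at its minimum of 8, split three ways, leaves fewer than 3 per cell, and a cell holding one arm only contributes nothing.
- SAP 10.0 sets a week with fewer than 4 diary days to missing, so assign a participant with one missing run-in week by the available week.
- Use the same strata in Step 3 of SAP 10.1.2.1.
- Keep the region-only CMH test as a sensitivity analysis.

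The cost is SAP and protocol wording and one derived variable. The downsides are some small strata and an odds ratio conditional on finer strata, which is not numerically comparable with the region-only one. Randomisation, diary, endpoint and sample size are unchanged.

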3.1. Study Rationale

Previous non-clinical and Phase 1 studies have shown relamorelin to have a potent prokinetic effect on the stomach, accelerating GE in both healthy volunteers and participants with diabetic gastroparesis (DG).

GP is a disorder characterized by signs and symptoms of nausea, abdominal pain, postprandial fullness, bloating, vomiting, and early satiety along with delayed GE, such that movement of food from the stomach to the small intestine takes longer than normal and occurs with unpredictable timing. Diabetes mellitus, either type 1 or 2 (T1DM or T2DM), is considered to be the most common identifiable cause of GP. This complication is a result of chronically elevated blood glucose levels, which are known to damage nerve structure and function. DG complicates management of blood glucose for both T1DM and T2DM patients due to carbohydrates being delivered to and therefore absorbed from the small intestine at variable times after ingestion. As a result, diabetic patients with DG often have poorly controlled diabetes, frequently with alternating hypo- and hyperglycemia, especially if treated with insulin.

In Phase 2 studies, the pharmacodynamic effect of relamorelin was confirmed in larger numbers of participants with DG, and in addition, beneficial effects on the symptoms of DG were observed. Safety and tolerability were shown at therapeutic doses, including the 10 µg twice daily (BID) dose to be studied in Phase 3 studies, supporting the decision to obtain confirmatory evidence of safety and efficacy of relamorelin in Phase 3, and specifically in Study RLM-MD-02.

A significant unmet medical need exists for a safe and effective treatment of patients with DG whose quality of life is impacted by their disease and for whom the current standard of care is

Relamorelin

suboptimal; therefore, the sponsor is performing this study to further the development of relamorelin for the treatment of DG.

3.2. Background

Relamorelin is being developed for the treatment of patients with DG to address the existing unmet need for an effective and safe/tolerable treatment, attested to by the FDA's granting of fast-track designation to relamorelin for the treatment of DG in adults. It is a member of an established class of compounds, ghrelin agonists, but if granted regulatory approval, will be the first member of this class to attain marketing approval.

In clinical studies to date, 466 participants with T1DM or T2DM with DG have been exposed to relamorelin at doses up to 100 µg administered BID by subcutaneous (SC) injection for 12 weeks.

In a randomized, placebo-controlled, multiple-dose Phase 2a study (RM-131-004), participants with T1DM and T2DM, and DG received 28 days of double-blind treatment with relamorelin. GE was accelerated and compared to placebo, relamorelin 10 µg BID significantly decreased the vomiting severity score and mean number of weekly vomiting episodes in participants with vomiting at baseline and produced improvement in the 4 individual DG symptoms of nausea, abdominal pain, bloating and early satiety as well as significant improvement in the composite endpoint of the 4 symptoms ($p=0.043$). The safety and tolerability profile of relamorelin in Study RM-131-004 was generally good.

The results in Study RM-131-004 helped the sponsor select the target patient population for enrolment in the Phase 2b Study RM-131-009, DG patients with vomiting at baseline, and encouraged assessment of a wider range of relamorelin doses.

Study RM-131-009 was a randomized, double-blind, placebo-controlled, stratified, multiple dose, multi-national study with 10 µg BID, 30 µg BID and 100 µg BID doses of relamorelin. A total of 393 participants with T1DM or T2DM, who had both delayed GE and moderate to severe symptoms of GP were enrolled and treated. The Phase 2b study confirmed a statistically significant effect of relamorelin over placebo on GE for the 10 µg and 30 µg doses. Vomiting frequency was reduced from baseline to Week 12 by approximately 75% in all relamorelin dose groups; however, there was also a strong, previously unobserved placebo effect on vomiting frequency (reduction of approximately 70%) that precluded statistical significance of the relamorelin effect that was observed. Results for the key secondary endpoint, a composite score of 4 DG symptoms (nausea, abdominal pain, bloating and early satiety) showed benefit of treatment with relamorelin compared to placebo although the difference was not statistically significant; the same was true for an exploratory endpoint, a composite score of 4 DG symptoms that included postprandial fullness instead of early satiety.

Relamorelin was generally safe and well tolerated among participants with T1DM or T2DM and DG. There were more reports of diarrhea and hyperglycemia-related events on relamorelin compared to placebo; hypoglycemia was infrequently reported (1.2% incidence in the placebo

Relamorelin

and relamorelin 100 µg groups only). Twenty-three serious adverse events (SAEs) were reported in the 289 participants treated with the 3 doses of relamorelin and 8 in the 104 participants treated with placebo. The number and characteristics of the reported SAEs reflected the advanced underlying disease state of this DG population with long-standing T1DM or T2DM and other common co-morbidities and only 2 of the SAEs (cardiac failure congestive and diabetes mellitus inadequate control) were assessed by the investigator as possibly related to study treatment, both in the 100-µg treatment group. Three adverse events (AEs) of diabetic ketoacidosis were reported, one event on each relamorelin dose. A total of 20 relamorelin-treated participants and 3 placebo-treated participants discontinued study treatment because of a treatment-emergent AE; only 3 in the relamorelin 10 µg BID group.

With respect to laboratory findings, in some participants glycemic control may have been negatively affected by the introduction of relamorelin. There were trends in increasing haemoglobin A1c (HbA1c) values after the initiation of relamorelin, which increased slightly after approximately 8 weeks, and dose-related trends in fasting hyperglycemia. Otherwise, no clinically relevant abnormalities were seen for other laboratory tests, including liver function tests, electrocardiograms (ECGs), physical examination findings, and injection site reactions; anti-drug antibodies (ADAs) were not found.

A detailed description of the chemistry, pharmacology, efficacy, and safety of relamorelin is provided in the investigator's brochure (Relamorelin Investigator's Brochure).

